8 STUDY ASSESSMENTS AND PROCEDURES

8.1 ENDPOINT AND OTHER NON-SAFETY ASSESSMENTS

The specific timing of procedures/evaluations to be done at each study visit are captured in Section 1.3, Schedule of Activities (SoA) including physical examination-based assessments, administration of

questionnaires and interviews, and collection of health care utilization data from the participant's EMR. Health Insurance Portability and Accountability Act (HIPAA) rules, other relevant federal or state laws, and local institutional requirements will be followed, as applicable.

Also, see Section 3 for a full list of Objectives and Endpoints.

8.2 SAFETY ASSESSMENTS

1. A Safety Monitoring Committee (SMC) will be formed to assure human subject safety and study integrity.
2. The PI and the study team will meet monthly to review all serious, unexpected and on-site AEs and make recommendations for any changes in reporting, consent or study activities.
3. A site visit program will 1) include an experienced data auditor who will review data to ensure that study procedures are understood and carried out correctly and 2) provide a mechanism to encourage the effective and standardized delivery of recruitment efforts, intervention programs, and the collection of appropriate and valid data. See MOP Chapter 14, Quality Control (QC), for additional information
4. We will minimize duloxetine-related risks by doing the following:
 - a. Study staff will administer a study medication Symptom Monitoring Form at five different occasions (weeks 1, 2, 4, 13 and 25) and will report every adverse effect (AE) to the medical safety officer (an internal medicine physician with active primary care clinic practice). For AEs that require medical attention, the medical safety officer will directly contact the participant to assess the need for adjustment or discontinuation of the study medication.
 - b. Participants will be assessed for suicidal ideation. The medical safety officer will be notified of low and moderate risk individuals and will direct study personnel how to proceed. Emergency procedures will be employed if a participant is considered high risk.
 - c. Urine pregnancy test will be performed at baseline (week 0) and at week 13 for all females of childbearing potential. We will ask pregnancy status at each study visit. We will ask subjects who become pregnant while in the study to discontinue duloxetine. These subjects will not be withdrawn from the study. Importantly, in the informed consent, we will include the rare side effects of Serotonin–norepinephrine reuptake inhibitor (e.g., duloxetine) exposure late in the third trimester.
 - d. The medical safety officer or the investigator will review AEs and determine likelihood that AEs are related to study drug.
5. Our trained study staff will ask about emotional distress related to the web-based CBT and report any concerning issues to the medical safety officer.
6. Data monitoring plan
 - a. Web-based scripted data entry forms will be utilized to guide staff through the administration of screening instruments administered via phone.
 - b. Once a subject passes screening and is formally enrolled in the study, study staff will use a custom data collection and randomization engine to collect demographic information, receive the randomization by stratum, and validate that inclusion and exclusion criteria have been appropriately tested.
 - c. Only the following people or organizations will be granted access to study records and data: study investigators, research team, Institutional Review Boards, the FDA, and the NIH (NINR).
 - d. Electronic case report forms (eCRFs) will be used for all data collection procedures. The data security measures will encompass the following functions:

- i) Data Tracking – will be used to provide the status of enrollment, number of complete data collection forms and number of forms.
- ii) Data Entry – systems will be in place to allow easy-to-use interfaces to minimize errors.
- iii) Data Editing – The need for data editing will be minimal because systems will be in place to prevent erroneous data entry.
- iv) Reporting – The study website will generate reports on a weekly basis of the number of patients enrolled, the number of missing data fields and the number of missing phone-delivered intervention sessions for the combination group (duloxetine + web-based CBT) with health care professional support. Periodic and ad-hoc reporting will be utilized to show subject recruitment and retention data.
- v) Statistical Analysis – The data management team will perform data analysis with SAS.
- f. Quality assurance (data integrity and validity) measures will be as follows:
 - i) Real-time data validation will be utilized to ensure data quality at the time of entry.
 - ii) Data and form checks will be completed by the WFDM team.
 - iii) Missing data will be monitored on a regular basis and the project manager on the study team side will be informed of missing data daily via “red flag” reminders in the database.
 - iv) The PI will discuss the rate and type of missing data during the bi-monthly teleconferences.
 - v) Data entry safeguards will prevent the erroneous entry of data that would fall outside the bounds of data that would be acceptable for a particular field.
 - vi) [name] will review weekly updates generated by the data management team to monitor missing data rates, and response times to red flag reminders.
- g. Data confidentiality will be ensured in the following ways:
 - i) Data will be used only in aggregate and no identifying characteristics of individuals will be published or presented.
 - ii) Alert values for medically relevant procedures (e.g., blood pressure, pulse rate, and suicidal ideation) will be developed, and a system will be in place to alert the medical study officer, depending on the urgency of the values.
 - iii) Confidentiality of data will be maintained by using research identification numbers that uniquely identify each individual.
 - iv) Safeguards will be established to ensure the security and privacy of participants' study records.
 - v) Appropriate measures will be taken to prevent unauthorized use of study information. Data other than demographic information will not use names as an identifier.
 - vi) Research records will be kept in a locked room at the research office.
 - vii) The files matching participants' names and demographic information with research ID numbers will be kept in a locked computer file (password protected) that uses a different key from that of all other files. Only trained and certified study personnel will have access to these files, and they will be asked to sign a document that they agree to maintain the confidentiality of the information.
 - viii) After the study is completed, local data will be stored with other completed research studies in a secured storage vault.
 - ix) In compliance with HIPAA and the Standards for Privacy of Individually Identifiable Health Information of the Department of Health and Human Services, we access personal health information and medical records only after receiving signed informed consent.

See MOP chapter 12, Safety Monitoring and Serious Adverse Events, for more details of the monitoring entity, monitoring procedures, and data monitoring plan.

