2.3 RISK/BENEFIT ASSESSMENT

2.3.1 KNOWN POTENTIAL RISKS

The risks primarily involve direct adverse effects of duloxetine which are well-described and minimal (i.e., sedation, nausea, headache, and dizziness that are typically transient in nature) in most individuals. For those who do not tolerate the side effects, the medication will be reduced or discontinued with an appropriate 7-day tapering regimen to prevent discontinuation syndrome. Side effects of these medications resolve shortly after stopping them.

Pregnant women are excluded from participation in this study. Because NO method of birth control is 100% reliable, a pregnancy test is required at baseline and at week 13. For subjects who become pregnant while in the study, duloxetine will be discontinued (with appropriate tapering regimen), and subjects will be allowed to continue with the study.

If a participant happens to become pregnant while in the study, the **rare** side effects of duloxetine for the fetus late in the third trimester include breathing difficulties, seizures, temperature instability, feeding difficulty, vomiting, low blood sugar, jitteriness, irritability, and tremor. To avoid unnecessary exposure to duloxetine, participants will get a repeat urine pregnancy test mid-way (week 13) during the 24 week study period. The enumerated side effects are side effects for the newborn.

Other potential risks include emotional distress related to the web-based pain coping skills training, which is typically a minor issue. Our trained research assistant, who collects information on medication

side effects, will be able to ask about emotional distress, with an agreed upon approach to refer participants to the medical safety officer if any concerns are present. Participants should discuss the risk of being in this study with the study staff.

There are no additional tests performed while enrolled in this study; however, a participant's study doctor may capture results of testing performed for normal clinical care.

Taking part in this research study may involve providing information that a participant considers confidential or private. Efforts, such as coding research records, keeping research records secure and allowing only authorized people to have access to research records, will be made to keep information safe.

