4 STUDY DESIGN

4.1 OVERALL DESIGN

PRECICE is a 24-week RCT of patients in the primary care clinics. During the study, participants will be randomized to one of three treatments: (1) [duloxetine + web-based CBT] with health care professional support, vs. (2) [duloxetine + web-based CBT] without health care professional support, vs. (3) duloxetine only. The primary purpose of the phone-based health care professional support is to enhance participant's motivation to engage in the web-based CBT program with regular practice of newly learned pain coping skills during and after the study. See section 9 for the analytical plan including sub-group analyses.

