8.3.4 TIME PERIOD AND FREQUENCY FOR EVENT ASSESSMENT AND FOLLOW-UP

The occurrence of an AE or SAE may come to the attention of study personnel during study visits and interviews of a study participant presenting for medical care.

All AEs, not otherwise precluded per the protocol, will be captured on the AE Form (included in MOP chapter 12, Safety Monitoring and Serious Adverse Events). Information to be collected includes event description, time of onset, clinician's assessment of severity, relationship to study procedures, and time of resolution/stabilization of the event. All AEs occurring while on study will be documented appropriately regardless of relationship. All AEs will be followed to adequate resolution or stabilization.

Any medical or psychiatric condition that is present at the time that the participant is screened will be considered as baseline and not reported as an AE. However, if the study participant's condition deteriorates at any time during the study, it will be recorded as an AE.

Changes in the severity of an AE will be documented to allow an assessment of the duration of the event at each level of severity to be performed. Documentation of onset and duration of each episode will be maintained for AEs characterized as intermittent.

Clinic staff and the study safety officer will record events with start dates occurring any time after informed consent is obtained. At each study visit, the investigator will inquire about the occurrence of AE/SAEs since the last visit. Events will be followed for outcome information until resolution or stabilization.

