10.1.6 SAFETY OVERSIGHT

Safety oversight will be under the direction of a SMC composed of individuals with the appropriate expertise, including two clinical investigators (one with expertise in clinical trials and the second with expertise in behavioral-based intervention) and one PHD level biostatistician. Members of the SMC will be independent from the study conduct and free of conflict of interest.

The SMC will meet twice a year and will be provided with a report that will contain safety data summaries, patient demographics and compliance data, recruitment, visit schedules, missed visits, outcomes and Medical Event Forms and any other AEs. Each member of the SMC will be given a detailed progress report at least two weeks before the meeting. The SMC will be able to request specific information and analyses from the PI's research team for monitoring purposes at any time during the study. Finally, the SMC will make recommendations to the PI regarding continuation, termination, or other modifications to the study based on observed AEs of the treatment under study. The PI will inform the NINR (National Institute of Nursing Research) project officer of any recommendations from the SMC. The NIH program officer will attend the SMC meeting on as needed basis.

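### The targeted staff question about emotional distress is tied to the web-based CBT, so distress reported to staff is not elicited equally in the duloxetine-only arm

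*Combined protocol and SAP*

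**What the plan says.** Section 8.2 treats the two kinds of treatment separately. Item 4 covers the risks of duloxetine, which every arm takes. Item 5 covers the web program: "Our trained study staff will ask about emotional distress related to the web-based CBT", with anything concerning passed to the medical safety officer. It gives no schedule for the question and no counterpart for an arm without CBT. Under section 4.1 the third arm receives duloxetine alone.

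Section 2.3.1 introduces the risk in the same way: "Other potential risks include emotional distress related to the web-based pain coping skills training, which is typically a minor issue". The next sentence is looser. It says that the research assistant who collects medication side effects "will be able to ask about emotional distress, with an agreed upon approach to refer participants to the medical safety officer". That sentence is permissive and does not mention CBT.

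On recording, section 8.3.4 says: "All AEs occurring while on study will be documented appropriately regardless of relationship". Section 8.3.3.1 makes the relationship to the intervention a separate classification, with categories from definite to not related. Section 10.1.6 has the SMC advise on continuing, modifying or ending the study "based on observed AEs of the treatment under study". Section 9.4.4 (Safety Analyses) reads N/A.

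**The concern.** Item 5 builds the presumed cause into the question, whereas sections 8.3.4 and 8.3.3.1 call for recording first and attributing afterwards. Followed literally, staff would put a targeted distress question to participants who have CBT and rely on more general routes for those who do not.

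Background distress is to be expected in this population. Section 4.2 anticipates coexisting depression, and section 9.1 states an exploratory hypothesis about comorbid psychological distress. If staff elicit distress more actively in two arms than in the third, the AE counts from those arms have no like-for-like control rate. There is also a participant-level side: a distressed person on monotherapy has one fewer written route to the medical safety officer.

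**Working it through.** The plan states no distress rate, detection rate or safety power, so there is no figure to reproduce. The check is mainly a reading of the text.

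**Step 1. Who is asked?** Under item 5 of section 8.2, only participants with CBT can answer the question, which means the two combination arms. Under the second sentence in section 2.3.1, the person asking has an all-arm task (side-effect collection) and the wording has no CBT limit, but the sentence directly follows one about CBT risk and says only that the assistant can ask. The two sections do not settle whether monotherapy participants are asked.

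**Step 2. What else covers monotherapy?**

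| Route | Where | Arms | What it leaves open |
|---|---|---|---|
| PHQ-8 and GAD-7, combined as PHQ-ADS | Table 1; section 9.4.9 | all | Given at weeks 0, 13 and 25, while CBT sessions run over 12 weeks (6.1.1); no stated rule turns a score into an AE record |
| Suicidal ideation assessment | 8.2, item 4b | all | Narrower and more severe than distress |
| AE/SAE inquiry at study visits | 8.3.4 | all | General, not targeted at distress |
| Symptom Monitoring Form, weeks 1, 2, 4, 13 and 25 | 8.2, item 4a; 6.1.1 | all | A study-medication form; its content is in the Manual of Procedures (MOP) and cannot be seen |

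So distress is sought in every arm, but the only staff question on it that the protocol spells out as something staff will ask is the CBT-related one.

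**Step 3. How large could the effect be?** This is illustration only; every rate is an assumption. Let p be the true distress rate, equal in all arms. Let a be the share that becomes a staff record in the combination arms, and b the share in monotherapy.

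- Recorded rates: p × a and p × b.
- Apparent ratio: a / b, whatever p is.
- Share missed in monotherapy relative to combination: 1 − b / a.

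Group sizes, assuming equal allocation (consistent with the 75 evaluable per group in section 9.2): 280 / 3 = 93.3 in monotherapy and 186.7 in the combination arms.

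With p = 10% and a = 90%:

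| b | Combination | Monotherapy | Ratio | Missed |
|---|---|---|---|---|
| 30% | 9.0% | 3.0% | 3.0 | 67% |
| 50% | 9.0% | 5.0% | 1.8 | 44% |
| 70% | 9.0% | 7.0% | 1.29 | 22% |
| 80% | 9.0% | 8.0% | 1.13 | 11% |
| 90% | 9.0% | 9.0% | 1.0 | 0% |

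At b = 50%, the expected counts are 186.7 × 0.10 × 0.90 = 16.8 and 93.3 × 0.10 × 0.50 = 4.7. For p from 5% to 20% and b from 30% to 70%, the false difference runs from 0.05 × (0.90 − 0.70) = 1 point to 0.20 × (0.90 − 0.30) = 12 points.

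The value of a is the weakest input. A question about distress caused by CBT would not pick up most background distress. If it raised capture only from 50% to 55%, the ratio would be 0.55 / 0.50 = 1.1. The direction is firmer than the size: the combination arms also get every all-arm route, so the extra question can only add to a. With one common question, a = b and the ratio is 1.0 for any p.

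**The case against.** Asking exposed participants about a known risk of their intervention is ordinary safety monitoring, and the rest of the plan limits any harm. Three stronger readings are tempting, and the documents support none of them.

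- **A reader might infer that distress is not sought in monotherapy at all.** Step 2 shows otherwise: all arms complete PHQ-8 and GAD-7, and all are asked about suicidal ideation and AEs. Section 2.3.1 may also extend the distress inquiry to everyone, and the unseen Symptom Monitoring Form may already contain a mood item.
- **A reader might infer that the trial will show combination treatment to be more distressing.** No safety analysis is planned, no endpoint is built on distress AEs, and the planned distress outcome, PHQ-ADS, is measured the same way in every arm. Item 5 sends only concerning issues to the medical safety officer, and attribution remains a separate step. The SMC includes a biostatistician and a behavioral-intervention expert and may request further analyses, so it cannot be presumed to read background distress as a CBT effect.
- **A reader might take 1.8 as an estimate.** It is only 0.90 / 0.50, and it assumes that a CBT-attributed question captures background distress at 90%, which sits badly with the restriction complained of.

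All of this narrows the point but does not remove it. The questionnaires do not produce AE records and leave gaps between administrations, general inquiry is not the same as a targeted question, and sections 8.2 and 2.3.1 still differ on who is asked.

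**Conclusion.** The point holds in limited form. As item 5 of section 8.2 is written, distress reported to staff, and any AE arising from it, is not elicited equally across arms, and section 2.3.1 does not match it. The effect is confined to SMC safety summaries, any by-arm AE listing, and referral of distressed monotherapy participants. The direction would be towards more recorded distress with combination treatment; the size cannot be found from the documents. No planned test and no efficacy figure is affected. This is an inexpensive improvement in harm ascertainment, not a demonstrated bias in a trial result. It rests on reading item 5 literally and on the MOP form having no arm-neutral mood item. If the form has one, what remains is to align the wording.

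**What to change.** 1. Replace item 5 of section 8.2 and the matching sentence in section 2.3.1 with one arm-neutral question to all participants, for example: *Since the last contact, have you had any emotional distress or worsening mood?* Ask it on the existing Symptom Monitoring Form schedule (weeks 1, 2, 4, 13 and 25). If the MOP form already has such an item, cite it and use it.
2. Record a positive answer first, then judge its relationship to CBT, support or drug as a separate step.
3. Base any by-arm statement about distress on this common item or on PHQ-ADS, not on reports from the CBT-framed question.

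The cost is a protocol wording amendment and at most one item on a form that every participant already completes, with no added visits. The downsides are a few more reports for the medical safety officer to review, and that participants seen before the change will lack the common item, so a by-arm summary of it would cover only later contacts.

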8.3 ADVERSE EVENTS AND SERIOUS ADVERSE EVENTS

8.3.1 DEFINITION OF ADVERSE EVENTS

An **adverse event** is any undesirable experience that occurs during the study, whether or not it is associated with the interventions in a participant.

8.3.2 DEFINITION OF SERIOUS ADVERSE EVENTS

An AE is **serious** if it results in death, is life-threatening, requires inpatient hospitalization or prolongs an existing hospitalization, results in a persistent or significant disability/incapacity, or might require medical or surgical intervention to prevent one of the outcomes, such as treatment in the emergency room for severe injurious falls.

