8.3.9 REPORTING OF PREGNANCY

See section 8.2 Safety Assessments for pregnancy related policy.

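### The SAE list has no birth-defect criterion, and Section 8.3.9 leads to no rule for reporting a pregnancy or recording its outcome

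*Combined protocol and SAP*

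**What the plan says.** Section 8.3.1 says that an adverse event "is any undesirable experience that occurs during the study, whether or not it is associated with the interventions in a participant". It names no fetus, newborn or offspring. Section 8.3.2 makes such an event serious if it "results in death, is life-threatening, requires inpatient hospitalization or prolongs an existing hospitalization", or if it "results in a persistent or significant disability/incapacity, or might require medical or surgical intervention to prevent one of the outcomes". Congenital anomaly and birth defect are not on the list.

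The whole of Section 8.3.9 on pregnancy reporting is "See section 8.2 Safety Assessments for pregnancy related policy". Item 4c of Section 8.2 sets urine tests at weeks 0 and 13, a question about pregnancy at each visit, discontinuation of duloxetine on pregnancy, and consent wording. Of participants who conceive it says "These subjects will not be withdrawn from the study". It sets no report, form, timeline or follow-up of the pregnancy.

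Section 2.3.1 ties a list of rare harms to the fetus late in the third trimester: "breathing difficulties, seizures, temperature instability, feeding difficulty, vomiting, low blood sugar, jitteriness, irritability, and tremor". It adds: "The enumerated side effects are side effects for the newborn". The synopsis puts each participant's time in the study at 25 weeks.

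**The concern.** The protocol recognizes that a participant may conceive on study drug, names harms to the newborn, and keeps her in the study. The reader then looks for the rule by which the outcome would be recorded. The cross-reference in 8.3.9 ends at a section that manages the participant but says nothing about how the pregnancy ends. The SAE list also omits the one criterion that is specific to offspring.

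What is at stake is the completeness of safety information, not any efficacy estimate. If a pregnancy is not logged when staff learn of it, and nobody is required to ask about it later, the outcome of an exposed birth cannot be reliably recovered after the trial.

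**Working it through.** The documents give no figure to reproduce. The check has two parts.

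**1. Timing of a birth against the end of participation**

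Inputs from the documents: tests at weeks 0 and 13 (8.2), a 7-day taper when a participant becomes pregnant (2.3.1), and participation ending at week 25 (synopsis). Assumptions not in the documents: birth 35 to 38 weeks after conception, and a pregnancy undetectable for about the first 2 weeks.

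- Earliest conception is week 0 − 2 = week −2. Earliest birth is −2 + 35 = week 33.
- Latest conception on study is week 25. Latest birth is 25 + 38 = week 63.
- Gap after the last visit: 33 − 25 = 8 weeks to 63 − 25 = 38 weeks.

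Every term birth therefore falls after participation ends, while 8.3.4 documents adverse events that occur on study.

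The same inputs bound exposure:

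- A pregnancy missed at week 0 and found at week 13 is at most 13 + 2 = 15 weeks from conception, or about 16 after the taper.
- One missed at week 13 was conceived no earlier than 13 − 2 = week 11, so it is at most 25 − 11 = 14 weeks from conception at week 25.
- Only if the week-13 test were missed or wrong could it reach 25 + 2 = 27 weeks from conception.

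Exposure within the trial would thus be mainly in early pregnancy.

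**2. Which route each kind of event would take**

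- *Pregnancy loss or maternal complication during the study.* This is an undesirable experience of the participant, so it is an adverse event under 8.3.1. It is serious if she is hospitalized or her life is threatened. It is covered.
- *Unexpected harm to the newborn that staff learn of.* The unanticipated-problem definition in 8.4.1 extends to others as well as subjects. If the event is possibly related and meets the other criteria, it is reportable under 8.4.2. It is covered once known.
- *Birth defect.* Section 2.3.1 does not name birth defects, so one could be unexpected and go by the same route. Section 8.4.2 sets 48 hours for an unanticipated problem that is an SAE and 7 calendar days for any other. Without a criterion in 8.3.2, a defect that is not serious on other grounds takes the 7-day clock.
- *Newborn harms named in 2.3.1.* Section 8.4.1 requires the event to be unexpected, meaning not described in the protocol or consent. These are described in the protocol, and 8.2 puts the rare effects of late third-trimester exposure in the consent. They would normally fail that test unless unusual in frequency or severity.
- *Any outcome after week 25.* No section requires anyone to ask.

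The one-year electronic-record extraction does not fill the gap. As specified in 9.4.9 it counts participants' referrals, specialty and allied-health visits, and orthopedic or musculoskeletal surgeries. It does not collect birth outcomes.

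**The case against.** A reader might infer that the definitions cannot capture any harm to a fetus or newborn, so that such harm would be neither recorded nor reported. The documents do not support that. Loss and complications in the participant are adverse events. The unanticipated-problem route reaches beyond subjects. Section 7.1 records the reason for stopping the intervention and has any new clinically relevant finding reported as an adverse event, which arguably includes a pregnancy that stops study drug. Section 8.3.4 follows recorded events to resolution or stabilization with no week-25 limit. The words about a participant in 8.3.1 come at the end of a loosely built sentence and need not be read as a strict exclusion.

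A reader might also infer that the named newborn harms are likely in this trial. Section 2.3.1 ties them to late third-trimester exposure and calls them rare. With two tests, a question at each visit and discontinuation on pregnancy, such exposure to study drug is unlikely. A precautionary repeat test is not a forecast of conceptions.

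Finally, Sections 8.2, 8.3.3.1, 8.3.4 and 8.3.5 place further detail in Manual of Procedures chapter 12, which may contain a pregnancy form.

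All of this narrows the point. It does not supply the missing criterion or an outcome rule. Section 7.1 does not say that a pregnancy is a reportable finding, and following a recorded event to resolution does not clearly mean following a pregnancy to birth. The unanticipated-problem route works only if someone hears of the event. Section 8.3.9 refers to 8.2, not to the Manual.

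**Conclusion.** The point holds as a gap in safety recording. Three things lack a dependable written route: a birth defect as a serious event, the newborn harms already named in 2.3.1, and any pregnancy outcome after week 25 that nobody is required to seek.

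Term births would come about 8 to 38 weeks after the last visit, given the assumed 35 to 38 weeks from conception to birth. A shorter gestation would narrow the gap, and a very preterm birth could fall within the study. The number of exposed pregnancies cannot be estimated from the documents and is probably small. No endpoint, contrast or power figure is affected. The conclusion rests on the protocol text alone, because Manual of Procedures chapter 12 was not available. The change is worth making because it is cheap and an outcome that nobody sought may not be recoverable later.

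**What to change.** - In 8.3.2, add as a seriousness criterion a congenital anomaly or birth defect in the offspring of a participant.
- In 8.3.1, state that events in the fetus or newborn of a participant exposed to study duloxetine are recorded.
- In 8.3.9, replace the bare cross-reference with two requirements: a pregnancy report when staff become aware of it, and one consented follow-up contact after the expected delivery date to record the outcome.
- Do not rely on the one-year record extraction. Besides not collecting birth outcomes, the newborn's chart belongs to another person, and some participants come from providers outside the health system.
- If chapter 12 of the Manual already has a pregnancy procedure, cite it in 8.3.9 and check that it covers the outcome.

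The cost is protocol and consent wording, a short form, and one contact past week 25 for the few cases. Dosing, eligibility and analysis are unchanged.
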